10.2.4.1 Primary Endpoint (Phase 2)

The primary endpoint of the Dose Expansion Phase (Phase 2) of the study is ORR per RECIST as assessed by the Investigator.

The ORR is the best overall response recorded from the start of the treatment until disease progression or recurrence.

The frequency and percentages of patients with a best overall response of CR, PR, stable disease (SD), or PD will be summarized. The confirmed response rate will also be summarized with frequencies and percentages.

10.2.4.2 Secondary Efficacy Endpoints

10.2.4.2.1 Overall Response Rate (ORR) based on Modified Response Criteria

The ORR based on the modified response criteria is the best overall response recorded from the start of the treatment until disease progression or recurrence as assessed by the Investigator using the modified RECIST criteria.

The frequency and percentages of patients with a best overall response of CR, PR, SD, or PD will be summarized.

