Appendix B: Modified RECIST Incorporating Immune-Related Response Criteria

Conventional response criteria may not be adequate to characterize the antitumor activity of immunotherapeutic agents like MPDL3280A, which can produce delayed responses that may be preceded by initial apparent radiological progression, including the appearance of new lesions. Therefore, modified response criteria have been developed that account for the possible appearance of new lesions and allow radiological progression to be confirmed at a subsequent assessment. In this protocol, patients will be permitted to continue study treatment even after modified Response Evaluation Criteria in Solid Tumors (RECIST) criteria for progressive disease are met if the benefit-risk ratio is judged to be favorable.

These modified criteria are derived from RECIST version 1.1 (v1.1) conventions and immune-related response criteria (irRC).

	RECIST v1.1	Modified RECIST
New lesions after baseline	Define progression.	New measurable lesions are added into the total tumor burden and followed.
Non-target lesions	May contribute to the designation of overall progression	Contribute only in the assessment of a complete response
Radiographic progression	First instance of $\geq 20\%$ increase in the sum of diameters or unequivocal progression in non-target disease	Determined only on the basis of measurable disease; may be confirmed by a consecutive assessment ≥ 4 weeks from the date first documented

Modified RECIST and RECIST, Version 1.1: Summary of Changes

RECIST = Response Evaluation Criteria in Solid Tumors.

Definitions of Measurable/Nonmeasurable Lesions

All measurable and nonmeasurable lesions should be assessed at screening and at the protocolspecified tumor assessment time points. Additional assessments may be performed, as clinically indicated for suspicion of progression.

Measurable Lesions

Tumor Lesions. Tumor lesions must be accurately measured in at least one dimension (longest diameter in the plane of measurement is to be recorded) with a minimum size as follows:

10 mm by CT or MRI scan (CT/MRI scan slice thickness/interval no greater than 5 mm);

10-mm caliper measurement by clinical examination (lesions that cannot be accurately measured with calipers should be recorded as nonmeasurable).

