All other lesions (or sites of disease), including pathological lymph nodes, should be identified as non-target lesions and should also be recorded at baseline. Measurements are not required.

It is possible to record multiple non-target lesions involving the same organ as a single item on the Case Report Form (CRF) (eg, "multiple enlarged pelvic lymph nodes" or "multiple liver metastases").

After baseline, changes in non-target lesions will contribute only in the assessment of complete response (ie, a complete response is attained only with the complete disappearance of all tumor lesions, including non-target lesions) and will not be used to assess progressive disease.

Calculation of Sum of the Diameters

A sum of the diameters (longest for non-nodal lesions, short axis for nodal lesions) for all target lesions will be calculated as a measure of tumor burden.

The sum of the diameters is calculated at baseline and at each tumor assessment for the purpose of classification of tumor responses.

Sum of the Diameters at Baseline: The sum of the diameters for all target lesions identified at baseline prior to treatment on Day 1.

Sum of the Diameters at Tumor Assessment: For every on-study tumor assessment collected per protocol or as clinically indicated, the sum of the diameters at tumor assessment will be calculated using tumor imaging scans. All target lesions and all new measurable lesions that have emerged after baseline will contribute to the sum of the diameters at tumor assessment. Hence, each net percentage change in tumor burden per assessment with use of modified RECIST accounts for the size and growth kinetics of both old and new lesions as they appear.

Response Criteria

Evaluation of Target Lesions

Complete Response (CR): Disappearance of all target lesions. Lymph nodes that shrink to < 10 mm short axis are considered normal.

Partial Response (PR): At least a 30% decrease in the sum of the diameters of all target and all new measurable lesions, taking as reference the baseline sum of diameters, in the absence of CR.

Note: The appearance of new measurable lesions is factored into the overall tumor burden but *does not automatically qualify as progressive disease* until the sum of the diameters increases by $\geq 20\%$ when compared with the sum of the diameters at nadir.

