Stable Disease (SD): Neither sufficient shrinkage to qualify for PR nor sufficient increase to qualify for PD, taking as reference the smallest sum of the diameters while on study.

Progressive Disease (PD): At least a 20% increase in the sum of diameters of all target and all new measurable lesions, taking as reference the smallest sum on study (this includes the baseline sum if that is the smallest on study). In addition to the relative increase of 20%, the sum must also demonstrate an absolute increase of at least 5 mm.

Impact of New Lesions on Modified RECIST

New lesions alone do not qualify as progressive disease. However, their contribution to total tumor burden is included in the sum of the diameters, which is used to determine the overall modified RECIST tumor response.

Evaluation of Best Overall Response Using modified RECIST

Timepoint Response

It is assumed that at each protocol-specified time point, a response assessment occurs. The following table provides a summary of the overall response status calculation at each time point for patients who have measurable disease at baseline.

Modified RECIST Time point Response Definition

% Change in Sum of the Diameters (Including Measurable New Lesions When Present)	Target Lesion Definition	Non-target Lesion Definition	New Measurable Lesions	New Unmeasurable Lesions	Overall Modified RECIST Timepoint Response
- 100% ^a	CR	CR	No	No	CR
- 100% ^a	CR	Non-CR or not all evaluated	No	No	PR
≤ - 30%	PR	Any	Yes or no	Yes or no	PR
> - 30% to < + 20%	SD	Any	Yes or no	Yes or no	SD
Not all evaluated	Not evaluated	Any	Yes or no	Yes or no	NE
≥+20%	PD	Any	Yes or no	Yes or no	PD

CR, complete response; NE, not evaluable; PD, progressive disease; PR, partial response; RECIST, Response Evaluation Criteria in Solid Tumors; SD, stable disease.

^a When lymph nodes are included as target lesions, the % change in the sum of the diameters may not be 100% even if complete response criteria are met since a normal lymph node is defined as having a short axis of < 10 mm. Any pathological lymph nodes (whether target or non-target) must have reduction in short axis to < 10 mm in order to meet the definition of CR.

Missing Assessments and Inevaluable Designation

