When no imaging/measurement is done at all at a particular time point, the patient is not evaluable (NE) at that time point. If only a subset of lesion measurements are made at an assessment, usually the case is also considered NE at that time point, unless a convincing argument can be made that the contribution of the individual missing lesion(s) would not change the assigned time point response. This would be most likely to happen in the case of PD. For example, if a patient had a baseline sum of 50 mm with three measured lesions and at follow up only two lesions were assessed but those gave a sum of 80 mm, the patient will have achieved PD status, regardless of the contribution of the missing lesion

Best Overall Response: All Time Points

The best overall response is determined once all the data for the patient are known. The best overall response according to modified RECIST is interpreted as below:

- **CR**: Complete disappearance of all tumor lesions (target and non-target) and no new measurable or unmeasurable lesions, confirmed by a consecutive assessment ≥ 4 weeks from the date first documented. All lymph nodes short axes must be < 10 mm.
- **PR**: Decrease in the sum of the diameters of all target and all new measurable lesions ≥ 30% relative to baseline, in the absence of CR, confirmed by a consecutive assessment ≥ 4 weeks from the date first documented.
- SD: Criteria for CR, PR, and PD are not met.
- **PD**: Increase in the sum of the diameters of all target and all new measurable lesions ≥ 20% relative to the nadir, which may be confirmed by a consecutive assessment ≥ 4 weeks from the date first documented as follows:

The confirmatory assessment shows an additional measurable increase in tumor burden as measured by the sum of the diameters of all target and all new measurable lesions.

This protocol allows patients to continue to receive study treatment even after confirmed radiographic PD per modified RECIST, and patients may achieve a best overall response of PR or CR based on tumor regression achieved at any time prior to study treatment discontinuation.

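### Modified-RECIST ORR has two different response windows: Section 10.2.4.2.1 stops at progression, while Appendix B counts responses until treatment stops, even after confirmed progression

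*Combined protocol and SAP*

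**What the plan says.** Section 10.2.4.2.1 takes the best response from treatment start "until disease progression or recurrence as assessed by the Investigator using the modified RECIST criteria". The window closes at progression.

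Appendix B, under best overall response, says that treatment may go on "even after confirmed radiographic PD per modified RECIST" and that "patients may achieve a best overall response of PR or CR based on tumor regression achieved at any time prior to study treatment discontinuation". CR and PR must be confirmed at least 4 weeks later. Confirmation of PD is optional; where it is done, "The confirmatory assessment shows an additional measurable increase in tumor burden".

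The opening of Appendix B gives the reason for these criteria: agents such as MPDL3280A, "which can produce delayed responses that may be preceded by initial apparent radiological progression, including the appearance of new lesions".

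The Phase 2 secondary objective (2.1.2), the endpoint list (2.2.2) and Section 10.2.4 all cite Appendix B for this endpoint. No text says which rule prevails.

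Two related rules matter:
- **DOR (10.2.4.2.2):** runs from the first record of response to the first documented PD, and adds that the first progression date is used for patients treated past progression.
- **DCR (10.2.4.2.3):** counts CR, PR or SD of at least 12 weeks, with no stated response window.

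**The concern.** The two windows can classify the same scans differently, and both texts govern the same endpoint. Followed literally, Section 10.2.4.2.1 discards some of the delayed responses that Appendix B says the modified criteria were developed to capture. The data can arise: Section 8.2.1 allows treatment past progression with efficacy assessments continuing, and Section 8.4.3.1 keeps scanning until all study treatment stops.

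The study is open-label and the response is Investigator-assessed. If the rule is left open, responder status for such patients could be settled after the data are seen.

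**Working it through.** No sample size, power or alpha is stated for this endpoint, so there is no figure of the plan to reproduce. The check compares the texts on constructed patients and then sizes the difference.

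**Thresholds (Appendix B).** PR is a fall of at least 30% from baseline in the total sum of diameters, new measurable lesions included. PD is a rise of at least 20% from the nadir, and "the sum must also demonstrate an absolute increase of at least 5 mm".

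**Patient 1: PD confirmed, then response.**

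| Week | Sum (mm) | Change | Status |
|---|---|---|---|
| 0 | 100 | | baseline |
| 6 | 130 | +30%, +30 mm | PD |
| 12 | 140 | a further +10 mm | PD confirmed |
| 18 | 65 | -35% | PR |
| 24 | 60 | -40% | PR confirmed, 6 weeks later |
| 27 | 60 | -40% | PR |
| 36 | 75 | +25%, +15 mm from nadir 60 | new PD |

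Section 10.2.4.2.1 gives best response PD, whether progression there means first or confirmed PD. Appendix B gives PR. Reading the word as confirmed PD therefore does not reconcile the texts.

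**Patient 2: PD never confirmed.** Sums of 50, 61 and 33 mm: 61/50 is +22% (+11 mm, PD), and 33/50 is -34% (PR, assumed confirmed). The texts differ only if Section 10.2.4.2.1 means the first, unconfirmed PD, which it does not say.

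**Patient 3: new lesion only.** Baseline 50 mm; week 6, target 45 + new lesion 10 = 55 mm (+10%, SD); week 12, 33 mm (-34%, PR), later confirmed. This is PR under both texts, because "New lesions alone do not qualify as progressive disease". Changes in non-target lesions count only towards CR "and will not be used to assess progressive disease", so they do not close the window either.

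**Patient 4: response off treatment, before PD.** Treatment stops without progression, and PR is first met on the EOT scan (Sections 8.2.2 and 8.4.3.1; the EOT visit is 28 days after last dose) or during the progression follow-up in Section 11.1. Section 10.2.4.2.1 counts it. Appendix B's literal window has already closed.

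**Size.** Planned numbers are from Section 10.3. The shift per affected patient is 1/n:
- Group A: 1/25 = 4.0 points; two patients, 8.0.
- Group B: 1/50 = 2.0 points; two patients, 4.0.
- Within Group B: T790M+ 1/30 = 3.3 points; T790M- 1/20 = 5.0 points.

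A patient like 1 raises the Appendix B rate over the Section 10 rate; a patient like 4 lowers it. The shift is larger if fewer patients are tumor evaluable.

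The documents give no rate q of first response after PD. As an assumption, the chance of at least one such patient is 1 - (1 - q)^n:

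| q | n = 25 | n = 50 |
|---|---|---|
| 1% | 22% | 40% |
| 2% | 40% | 64% |
| 5% | 72% | 92% |
| 10% | 93% | 99.5% |

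**DOR for Patient 1, if counted as a responder.** The first sentence of Section 10.2.4.2.2 can be read as ending DOR at the PD after response: day 252 - day 126 = 126 days. The second sentence could be read as ending it at the PD on day 42, before the response began.

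**PFS for Patient 1.** Under Section 10.2.4.2.4 it is 1 + 42 = 43 days under either response window.

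**The case against.** The best defense is that the intended rule is clear enough. The objective, the endpoint and Section 10.2.4 name Appendix B, and Section 10.2.4.2.1 itself invokes the modified criteria. Appendix B holds the specific rule, while Section 10.2.4.2.1 repeats the generic sentence of the primary endpoint. An analyst has good grounds to follow Appendix B. This lowers the risk but does not remove the conflict: the Section 10 sentence names progression as its end, and no precedence is stated.

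It is also fair that the weight is limited. The endpoint is descriptive, with no test or decision attached, and treatment past progression needs case-by-case Sponsor approval (8.2.1).

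Four stronger readings are tempting but not supported:
- **Every response after apparent progression is lost.** Patient 3 shows otherwise.
- **Only post-progression responders are affected.** Patient 4 is a second group, with the opposite sign.
- **The plan produces a negative DOR** (day 42 - day 126 = -84 days for Patient 1). That needs an Appendix B response combined with one reading of Section 10.2.4.2.2. Under Section 10 taken consistently, this patient is a non-responder and has no DOR. The supported statement is that the rule is ambiguous.
- **DCR contradicts Appendix B.** Section 10.2.4.2.3 is silent on the window. Read alone, it would count the late PR.

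**Conclusion.** The concern holds as a wrong stated rule for one descriptive secondary endpoint. Section 10.2.4.2.1 and Appendix B disagree on when the modified-RECIST response window closes, and no reading of progression reconciles them. Each affected patient moves that ORR by 4.0 points in Group A or 2.0 points in Group B, assuming all planned patients are tumor evaluable. How many there will be is unknown and may be zero. DOR for post-progression responders is ambiguous, and the DCR response window is unspecified.

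The primary RECIST v1.1 ORR is not affected, since Section 10.2.4.1 and Appendix A both stop at progression. Nor are the futility rules, read as using that primary ORR, or PFS, which uses the first progression date. The point should be fixed before analysis.

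**What to change.** Before analysis:

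1. **10.2.4.2.1, modified RECIST.** Replace the progression cut-off with the Appendix B window: a CR or PR confirmed at least 4 weeks later counts if reached before study treatment discontinuation, including after PD. Keep counting responses first seen after discontinuation but before PD, as the section now does, with an added limit at new anticancer therapy. State that the confirmatory scan may fall after discontinuation if it precedes new anticancer therapy.
2. **10.2.4.2.2.** For modified RECIST only, end DOR at the first modified-RECIST PD after the first response date. Keep the current rule for RECIST v1.1.
3. **10.2.4.2.3.** State that the CR/PR part of modified-RECIST DCR uses the same response window.
4. **PFS.** Leave it at first progression, and disclose that for post-progression responders DOR begins after the PFS event.
5. **Reporting.** Give the number of post-progression responders separately, noting any response first seen after on-study local treatment of a lesion, which Section 7.1 allows.

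The cost is minor wording and programming, with no new scans. The downside is that DOR and PFS run on different clocks for these patients, so the disclosure is needed.

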10.2.4.2.2 Duration of Response (DOR)

Duration of response for CR and PR will be measured from the date that any of these best responses is first recorded until the first date that PD is objectively documented. For patients who continue treatment post-progression, the first date of progression will be used for the analysis. Patients without a documented event of radiographic progression will be censored on the date of the most recent tumor assessment.

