2.2.2 Secondary Endpoints

The following are the secondary endpoints for this study:

- ORR according to modified RECIST incorporating irRC (Appendix B);
- Duration of response, DCR, and PFS according to RECIST v1.1 (Appendix A) as determined by Investigator assessment;
- Duration of response, DCR, and PFS according to modified RECIST incorporating irRC (Appendix B);
- Overall survival (OS);
- Change from baseline in mutant EGFR levels in circulating tumor DNA (ctDNA) obtained from plasma.

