10.2 Statistical Methods

10.2.1 General Considerations

Data will be summarized using descriptive statistics (number of patients, mean, median, standard deviation, minimum, and maximum) for continuous variables and using frequencies and percentages for discrete variables. Data will be presented by dose cohorts, as appropriate.

Kaplan-Meier methodology will be used to summarize time to event variables.

All data will be used to their maximum possible extent but without any imputations for missing data.

All statistical analyses will be conducted with the Statistical Analysis Software (SAS[®]) system.

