10.2.4 Efficacy Analyses

The efficacy endpoints of ORR, DoR, DCR, and PFS will be evaluated using RECIST v1.1 (Appendix A:) and modified RECIST incorporating irRC (Appendix B). Efficacy endpoints evaluated by the Investigator will be presented for the subgroup of patients determined to be tumor evaluable by the Investigator.

Progression-free survival and OS will also be presented for the safety population.

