10.2.4.2.4 Progression-Free Survival (PFS)

Progression-free survival (PFS) will be calculated as 1+ the number of days from the first dose of study drug to documented radiographic progression, as determined by the Investigator or death due to any cause, whichever occurs first. Patients without a documented event of radiographic progression will be censored on the date of their last adequate tumor assessment (ie, radiologic assessment) or date of first dose of study drug if no tumor assessments have been performed.

For patients who continue treatment post-progression, the first date of progression will be used for the analysis of PFS.

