10.2.4.2.5 Overall Survival

Overall survival (OS) will be calculated as 1+ the number of days from the first dose of study drug to death due to any cause. Patients without a documented date of death will be censored on the date the patient was last known to be alive.

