Duration of Overall Response

The duration of overall response is measured from the time measurement criteria are met for CR or PR (whichever is first recorded) until the first date that recurrent or PD is objectively documented (taking as reference for PD the smallest measurements recorded since the treatment started).

The duration of overall CR is measured from the time measurement criteria are first met for CR until the first date that recurrent disease is objectively documented.

Duration of Stable Disease

SD is measured from the start of the treatment until the criteria for progression are met, taking as reference the smallest measurements recorded since the treatment started.

Reference:

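### Duration of response has no rule for death: a responder who dies without a progression scan is censored at the last scan, while the same death is a PFS event (minor)

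*Combined protocol and SAP*

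**What the plan says.** Section 10.2.4.2.2 measures DOR from the first recorded response to the first objectively documented progression. Its censoring sentence covers everyone else: "Patients without a documented event of radiographic progression will be censored on the date of the most recent tumor assessment". The duration text in Appendix A runs "until the first date that recurrent or PD is objectively documented" and does not mention death either. Section 10.2.1 names the estimator: "Kaplan-Meier methodology will be used to summarize time to event variables".

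The PFS definition in Section 10.2.4.2.4 ends at radiographic progression "or death due to any cause, whichever occurs first". Its censoring sentence nevertheless has the same form as the one for DOR: "Patients without a documented event of radiographic progression will be censored on the date of their last adequate tumor assessment".

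The single DOR definition serves two secondary endpoints. Section 10.2.4 states "The efficacy endpoints of ORR, DoR, DCR, and PFS will be evaluated using RECIST v1.1" and adds the modified criteria, and Section 2.2.2 lists "Duration of response, DCR, and PFS according to modified RECIST incorporating irRC" alongside the RECIST v1.1 version.

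The documents disagree on how long scanning lasts. The synopsis and Section 8.4.3.1 end tumor assessments with study treatment, apart from the end-of-treatment scan. Section 8.3 and Table 1 note CC then collect only survival and subsequent therapy. Section 11.1 follows patients for progression every 8 ± 1 weeks until it occurs.

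**The concern.** Read as written, the plan treats one death in one patient as an event for PFS and as a censoring for DOR, and gives no reason. Kaplan-Meier estimation assumes that patients censored at a given time have the same outlook as those still followed. A responder censored because of death may have had unscanned progression or toxicity, so that assumption is doubtful for this group.

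Section 1.5 argues for the combination partly on the prospect of durable responses, and DOR is the endpoint that describes durability. A reader of the results would reasonably expect DOR and PFS to handle death in the same way.

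**Working it through.** The plan states no DOR figure, so there is none to reproduce. The check compares the written rule with a progression-or-death rule.

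**One death, exact Kaplan-Meier.** Let n responders be at risk at the patient's last scan, and let k others progress between that scan and the death.
- During the gap: written rule (n−1−k)/(n−1); progression-or-death (n−k)/n.
- After the death: written rule (n−1−k)/(n−1); progression-or-death (n−k−1)/n.
- With n = 10 and k = 2: 77.8% against 80.0% during the gap, then 77.8% against 70.0% after the death.

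So the written rule is lower during the gap if k is at least 1, and higher afterwards. The direction at a fixed time depends on the gap.

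**Model inputs, all assumed.** Median time m to progression or end of scanning: 9 months. Share q of responders who stop without progression and then die: 2% to 20%. Gap from last scan to death: varied. The nearest figure in the documents is in Section 1.3.1: 11 on-study deaths among 148 monotherapy patients, 8 of them attributed to progression. That leaves 3/148 = 2.0%. It is only a loose guide, since it covers all treated patients rather than responders, and a progression death may also lack a scan.

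**Formulas**, with L = ln 2/m = 0.0770 per month:
- Written rule: S(t) = exp(−(1−q)Lt).
- Progression-or-death, no gap: S(t) = exp(−Lt).
- Progression-or-death, exponential gap with mean g: S(t) = exp(−Lt) + qL·exp(−t/g)·[exp((1/g−L)t)−1]/(1/g−L).
- Progression-or-death, fixed gap d with t ≤ d: S(t) = exp(−Lt) + q[1−exp(−Lt)].

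**12-month DOR, no gap.** Progression-or-death gives 39.7%. The written rule gives 40.4%, 41.6%, 43.5% and 47.7% at q = 2%, 5%, 10% and 20%. The differences are +0.7, +1.9, +3.8 and +8.1 points.

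**Longer gaps** (exponential; difference in points, written rule minus progression-or-death):

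| q | mean gap 6 months | 12 months | 24 months |
|---|---|---|---|
| 5% | +0.75 | +0.1 | −0.4 |
| 10% | +1.6 | +0.3 | −0.7 |
| 20% | +3.6 | +1.0 | −1.1 |

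For q of 5% to 20% and m of 6 to 12 months, the sign changes at a mean gap of about 9 to 22 months.

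**Dependence on the gap distribution.** With a fixed 12-month gap and q = 20%, progression-or-death gives 0.397 + 0.2 × 0.603 = 51.8%. The difference is −4.0 points, against +1.0 for an exponential gap with the same mean. With a fixed 18-month gap the medians are 9/0.8 = 11.25 months (written rule) and ln(1/0.375)/L = 12.7 months.

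**Simulation on a scan grid.** Using 400,000 responders, scans every 6 and then 9 weeks, and the 10.4-month monotherapy median PFS borrowed as the time scale, deaths on the scan schedule gave 12-month DOR of 47.9% against 46.0% (q = 5%), 47.6% against 43.8% (10%) and 47.3% against 39.2% (20%). The pattern is the same.

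**Precision.** Section 10.3 implies about 25 × 0.5 = 12.5 responders in Group A and 30 × 0.5 = 15 among T790M+ patients at a 50% ORR. The standard error of an estimate near 50% is √(0.25/12.5) = 14.1 or √(0.25/15) = 12.9 points.

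**The case against.** The strongest reply is that the written rule estimates something coherent, namely time to documented progression. In the model above, progression and stopping without progression are unlinked, so the censoring is non-informative for that quantity. The figures are then differences between two endpoint definitions, not bias. This stands. A reader might infer that informative censoring has been demonstrated, but the documents contain no data that would show it.

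A reader might also infer that the rule simply inflates DOR. The documents do not support a fixed direction, because they do not settle how long scanning continues. After a long gap, a progression-or-death rule credits an unscanned patient with progression-free time until death, and it is then the alternative that lengthens DOR.

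A third tempting inference is that PFS also censors deaths, since its censoring sentence omits them. Section 10.2.4.2.4 names death as an event first, so this is a wording fault only.

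Finally, deaths are not hidden: PFS counts them, and PFS and OS are also presented for the safety population. That limits the severity but does not supply a death rule for DOR. That Appendix A is a summary of a published guideline is a reason to place the study rule in Section 10.2.4.2.2; it is not a reason to leave the rule out.

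**Conclusion.** The defect is real and minor. As written, a responder's death without a progression scan is a censoring for both DOR endpoints and an event for PFS. If such deaths fall soon after the last scan, 12-month DOR is about 2, 4 or 8 points higher than under progression-or-death at shares of 5%, 10% or 20%, and under 1 point higher at 2%. With long gaps the difference shrinks and can reverse, by an amount that depends on the assumed gap distribution. The share, the gap and the median are all assumptions, and if no responder dies this way there is no effect. Over these shares the differences are smaller than the 13 to 14 point standard error. No test, threshold or decision rests on DOR.

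**What to change.** In Section 10.2.4.2.2, define DOR as the time from first response to the earlier of first documented progression or death from any cause. Censor at the last tumor assessment only responders with neither. Specify in advance that deaths after new anticancer therapy, or after a long unscanned gap of stated length, are censored at the last tumor assessment, either in the main analysis or in a mandatory sensitivity analysis. State that this rule governs over the Appendix A summary.

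As a wording repair, limit PFS censoring in Section 10.2.4.2.4 to patients with neither progression nor death.

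Separately, reconcile the synopsis, Sections 8.3 and 8.4.3.1 and Table 1 note CC with Section 11.1 on progression follow-up after treatment stops, since this determines how long the gap can be.

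The cost is a few clauses and one extra analysis run. Survival status and subsequent therapies are already collected under Section 8.3, and Section 10.2.4.2.5 already uses death dates for OS, so the definition changes need no new data. DOR estimates may become shorter or, with long gaps, longer. Depending on how the follow-up sections are reconciled, some assessments after treatment may be added.
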